NCT04287517 17.03.2020

Efficacy of Capacitive-Resistive Therapy on the Treatment of Myofascial Pain

Study Protocol and Statistical Analysis Plan

NCT04287517 17.03.2020

Material and Methods

Thirty six volunteers with active myofascial trigger points in the upper trapezius and neck were included the study after being examined by sports medicine specialists between 12 December – 1 March. During the examination, the reproduction of the daily life complaints and the presence of a tense muscle band, hypersensitive point, which was characterized by reflected pain and local twitch findings, was evaluated diagnostically. Exclusion criteria were fibromyalgia, discal hernia, radiculopathy, myelopathy, having received trigger point injection and physical therapy within the last 1 month, neck or back surgery, rheumatismal diseases, pregnancy. The study was approved by the Istanbul Faculty of Medicine Ethics Committee. All participants were informed of the study and signed written informed consent. The study was designed as a prospective, randomized, placebo-controlled double-blind trial (NCT04287517). The patients were divided into two groups by a physician who did not participate in patient evaluation using the block randomization method. The Sports Physician who made the evaluations carried out blindly until all data was collected. Patients likewise received their treatment blindly at different times throughout the entire study. The entire randomization process was carried out in accordance with Consort Statement.

Treatment

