Normal joint movements of the cervical region are important for many activities in daily life. In our study, inclinometer was preferred for the evaluation of cROM. Evaluation of passive joint movements in the cervical region is also used to determine the capsular pattern and final sensation of the joint. In the previous study, the ICC value was found to be 0.89 - 0.94 with the inclinometer. Flexion, extension, lateral rotation in both directions and flexion ROM examinations were performed. The normal cervical spine's range of motion is approximately 80° to 90° of flexion, 70° of extension, 20° to 45° of lateral flexion, and up to 90° of rotation to both sides.

Statistical Analysis Plan

Average values were compared statistically. Evaluations were made both within the group before and after treatment (TO) and also for intergroup before and after treatment. Descriptive statistics of the numerical variables in the study are given as mean, median, min-max, standard standard deviation. Descriptive statistics for categorical variables were given as numbers and percentages. Numerical variables were analyzed with the Shapiro Wilk test. Student t Test was used for group comparison of variables with normal distribution, and Mann Whitney U test was used for group comparisons of non-normally distributed variables. For dependent groups, Paired t Test was used for mean comparisons and Wilcoxon test was used for median comparisons. In calculations, 0.05 was taken as the level of significance. SPSS (version 21) package program was used in the analysis.

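### A normality test on the trial's own data picks the t test or Mann-Whitney for each outcome, and neither comparison uses the baseline value

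*Combined protocol and SAP*

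**What the plan says.** The Statistical Analysis Plan states that "Numerical variables were analyzed with the Shapiro Wilk test". It continues: "Student t Test was used for group comparison of variables with normal distribution". Outcomes judged not to be normal go to Mann-Whitney instead. For within-group change it says "For dependent groups, Paired t Test was used for mean comparisons and Wilcoxon test was used for median comparisons". The significance level is 0.05.

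The same section opens by saying that averages were compared, within groups and between groups, before and after treatment. The Outcomes section lists VAS, NDI, SF-36, range of motion and pressure pain threshold, all measured before and after treatment. Material and Methods gives the size: "Thirty six volunteers with active myofascial trigger points in the upper trapezius and neck were included the study".

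The plan does not say at what cut-off the Shapiro-Wilk test is read. Nor does it say whether it is applied to all 36 values, to each arm, to change scores or to residuals. It names no single between-group test for any outcome.

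**The concern.** Three things follow from the text.

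- **The hypothesis is left open.** The t test compares means. Mann-Whitney compares ranks and does not test a difference in means, although the section says that averages are compared. An outcome could be judged by means before treatment and by ranks after it, and two outcomes in one results table could answer different questions. Because the cut-off and the object of the pre-test are not given, two analysts could follow the plan and report different tests for the same outcome.
- **The baseline value is not used.** The between-group comparisons read as separate comparisons at each time point. Neither branch adjusts the after-treatment comparison for baseline. In a trial of 36 patients that costs precision.
- **The paired rule selects nothing.** The plan ties the paired t test to means and the Wilcoxon test to medians, but it reports both mean and median for every numerical variable, so either test, or both, would comply.

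**Working it through.** The plan gives no power calculation, effect size, SD or distribution, so it has no figure of its own to reproduce beyond the 0.05 level.

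**Inputs from the document:** 36 patients in two block-randomized groups; Shapiro-Wilk, then t test or Mann-Whitney; level 0.05.

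**Assumptions:** 18 per arm (the ratio is not stated), two-sided tests, Shapiro-Wilk read at 0.05, no dropout, the outcome shapes below, and for power a true difference d = 0.8 SD and baseline correlation r = 0.5.

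**Step 1. Selection and overall error, no true difference.** There were 20,000 simulated trials per shape. The pre-test was run three ways: on the pooled 36 values / on each arm (both must pass) / on residuals.

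| Shape (skewness) | t test chosen, % | Type I error of whole rule, % |
|---|---|---|
| normal (0) | 95 / 91 / 95 | 5.1 / 5.2 / 5.3 |
| gamma 16 (0.5) | 83 / 81 / 84 | 4.9 / 5.2 / 5.2 |
| gamma 8 (0.7) | 71 / 71 / 73 | 5.1 / 5.6 / 5.6 |
| gamma 4 (1.0) | 47 / 54 / 51 | 5.0 / 5.5 / 5.5 |
| gamma 2 (1.4) | 16 / 28 / 22 | 4.7 / 5.4 / 5.4 |

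The Monte Carlo standard error of the last column is about 0.15 percentage points. Across all runs made for this point the range was about 4.6 to 5.9%. With a 20/16 split at gamma 4 (per arm), the t test was chosen in 55% of trials and the overall error was 5.4%.

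**Step 2. Disagreement when there is a true difference.** At d = 0.8 the t test and Mann-Whitney gave different verdicts in about 7% of trials (normal), 10% (gamma 4) and 12 to 13% (gamma 2).

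**Step 3. What ignoring baseline costs.** For normal data this can be checked by hand.

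- Unadjusted t test: noncentrality d × √(n/2) = 0.8 × √9 = 2.40 on 34 df, giving power of about 65%.
- Baseline-adjusted: residual variance is multiplied by 1 − r² = 0.75. Chance baseline imbalance multiplies it by about 1 + 1/(36 − 4) = 1.031. The effective difference is 0.8/√(0.75 × 1.031) = 0.91 and the noncentrality is 0.91 × 3 = 2.73 on 33 df, giving power of about 76%.

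Simulated power at d = 0.8, r = 0.5:

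| Shape | Fixed t test | Two-stage rule | Baseline-adjusted model |
|---|---|---|---|
| normal | 65% | 65% | 76% |
| gamma 4 | 65% | 68 to 69% | 76% |
| gamma 2 | 65% | 74% | 74% |
| exponential | not run | 84 to 85% | 75 to 78% |

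For exponential data the two-stage rule is almost always Mann-Whitney, since the t test passes a per-arm pre-test in only about 5% of null trials. Entries for skewed shapes can move by a few points with the way the correlated baseline is generated.

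**Step 4. Does the replacement hold its level?** With no true difference, gamma outcome of skewness 1 and r = 0.5, the baseline-adjusted model rejects in 4.9% of trials.

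**The case against.** The strongest reply is that the rule does little harm, and much of that stands.

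A reader might infer that the chosen t test does not hold its 5% level. That is true only among trials that pass the pre-test, and mainly if the pre-test is run per arm or on residuals: 6.2% and 6.7% at gamma 4, 8.0% and 10.9% at gamma 2. On the pooled 36 values, which the wording permits, the figures are 5.5% and 5.7%. The level in the plan governs the whole rule, where the excess nearly cancels. At gamma 2, per arm: 0.276 × 8.00% + 0.724 × 4.35% = 2.21% + 3.15% = 5.4%.

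A reader might also infer that the choice of test is a coin toss. It is close to that only around skewness 1.0 to 1.2. Elsewhere selection follows shape, and the document gives no distribution for any outcome.

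It is tempting to credit the power gain to dropping the pre-test. On normal data a fixed t test and the two-stage rule have the same power, and under skew the two-stage rule does better than a fixed t test. The gain comes from baseline adjustment. Nor is the missing baseline a fault of the rank branch alone; the t branch as written omits it too.

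For the paired tests, one might infer that normality is checked on raw values instead of within-patient differences. The text does not link the Shapiro-Wilk test to the paired tests, so only the absence of a usable rule can be claimed.

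Finally, any two valid tests disagree sometimes, so 7 to 13% is no evidence of bias. It does show that the choice can change a conclusion, which is a reason to settle it beforehand.

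If the between-group comparison was meant to be of change scores, baseline would enter. At r = 0.5, however, the variance of a change is 2(1 − r) = 1 times that of the after-treatment value, so nothing is gained over ignoring baseline.

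**Conclusion.** The concern holds as a gap in specification and a loss of precision. It does not hold as a claim of inflated error. The test and hypothesis for each outcome depend on a normality result in the trial's own data, under a rule whose details are not given. The paired rule is undefined, and the between-group comparisons leave out the baseline.

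Its size rests on the assumed shapes, equal arms, d = 0.8 and r = 0.5. The choice of test changes the verdict in roughly one trial in fourteen (7%) to one in eight (13%). Baseline adjustment adds about 76 − 65 = 11 percentage points of power on normal data and about 76 − 69 = 7 at gamma 4. It adds nothing at gamma 2 and loses power for exponential data. A lower correlation than 0.5 would shrink the gain and a higher one would enlarge it.

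This is a worthwhile and cheap improvement. It does not by itself invalidate the trial's comparisons.

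**What to change.** In the Statistical Analysis Plan:

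1. Delete the rule by which the Shapiro-Wilk test selects the between-group test.
2. For every outcome, make the main between-group analysis a linear model of the after-treatment value on group and that outcome's baseline value. Report the adjusted difference with its confidence interval.
3. Check normality on the model residuals, as a diagnostic that does not change the main analysis.
4. Report Mann-Whitney on change scores for every outcome as a fixed sensitivity analysis that does not replace the main result.
5. If within-group change is still described, name one paired method and use it throughout.

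The cost is a paragraph of text and a few lines of SPSS syntax, with no new data. The downside is power for a strongly skewed outcome: about 78% for the linear model against 84 to 85% for the rank test with exponential data (one run put the model at 75%). The fixed sensitivity analysis keeps that result visible. The plan is written in the past tense, so if outcome data have already been seen, the report should say that the model was adopted afterwards.

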After the patients were divided into two groups, capacitive resistive therapy and exercise were applied to one group, and placebo (sham) therapy and exercise were applied to the other group by an experienced physiotherapist for 10 sessions. The sessions were continued for 3 weeks with an interval of 24-48 hours. All sessions were planned for 16 minutes (8 minutes to one side and 8 minutes to the other). Individuals who received a placebo treatment were administered sham in empty mode without energy transfer. The patients were reported not to understand that they received a placebo they were working without heating the system. In each session ten minutes capacitive mode six minutes resistive mode was used. Since myosfacial trigger points are predominantly located in superficial muscle tissue, capacitive therapy was preferred. It was also benefited from resistive treatment to achieve deep tissue effect. Physiotherapist after applying capacitive and resistive therapy or placebo to patients; The patients performed neck stretching exercises (for Trapezius and Levator Scapula muscles) and isometric neck exercises 10 repetitions and 3 sets. Each exercise was carried out under the supervision of the same physiotherapist, after each session.

Outcomes

Visual Analog Scale (VAS), neck disability index (NDI), short form - 36 (SF-36) questionnaire, ROM and algometer, Pain Pressure Threshold (PPT), were evaluated blindly by an experienced sports medicine clinician before and after the treatment. In each evaluation, all measurements were repeated 3 times and their averages were calculated at the end. VAS, SF-36 and Neck Disability Index were filled under supervision before each individual started treatment. Subsequently, neck range of motion (ROM) measurement were performed with inclinometer and Pain Pressure Threshold measurement were performed with the algometer.

Pain intensity was evaluated by VAS and Algometer. VAS: A tool used to help a person rate the intensity of certain sensations and feelings, such as pain. The visual analog scale for pain is a straight line with one end meaning no pain and the other end meaning the worst pain imaginable. A patient marks a point on the line that matches the amount of pain he or she feels. The most simple VAS is a straight horizontal line of fixed length, usually 100 mm. The ends

NCT04287517 17.03.2020

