are defined as the extreme limits of the parameter to be measured (symptom, pain, health; in this study pain will be studied) orientated from the left (worst) to the right (best). Lower scores mean better outcome. The validity and reliability study of the scale was determined by Price et al. It has a good degree of validity and reliability. PPT is defined as the minimum force applied which induces pain. This measure has proven to be commonly useful in evaluating tenderness symptom. It has been shown to be a reliable method of evaluating myofascial trigger points. Studies have shown high consistency among clinicians (ICC 0.80 - 0.92).

NDI was used for neck disability assessment. Vernon et al. developed NDI as the neck version of Oswestry Low Back Pain Scale. Turkish version of the study was made by Aslan et al. The test-retest reliability value of the questionnaire was found ICC: 0.979 (excellent). Neck Disability Index (NDI) is a self-report questionnaire used to determine how neck pain affects a patient's daily life and to assess the self-rated disability of patients with neck pain. Each question has six statement, the first statement is marked the section score = 0, if the last statement is marked it = 5. Maximum score is 50 and minimum is 0. Lower scores mean better outcome.

The Short Form (36) Health Survey is a 36-item, patient-reported survey of patient health. The SF-36 is a measure of health status and an abbreviated variant of it. The SF-36 consists of eight scaled scores, which are the weighted sums of the questions in their section. Each scale is directly transformed into a 0-100 scale on the assumption that each question carries equal weight. The lower the score the more disability. The higher the score the less disability i.e., a score of zero is equivalent to maximum disability and a score of 100 is equivalent to no disability.

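### No primary outcome, testing order or multiplicity rule is named: with an assumed 5 to 17 between-group tests, the chance of a false result favouring active treatment is about 9% to 19% at correlation 0.5, against 2.5% for one test

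*Combined protocol and SAP*

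**What the plan says.** The Outcomes section introduces all the measures in one sentence and gives none of them precedence: "Visual Analog Scale (VAS), neck disability index (NDI), short form - 36 (SF-36) questionnaire, ROM and algometer, Pain Pressure Threshold (PPT), were evaluated blindly". Pain itself is given two measures: "Pain intensity was evaluated by VAS and Algometer".

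Two of the five instruments yield several scores. For the questionnaire, "The SF-36 consists of eight scaled scores". For range of motion, "Flexion, extension, lateral rotation in both directions and flexion ROM examinations were performed"; the reference ranges that follow also mention "20° to 45° of lateral flexion, and up to 90° of rotation to both sides". The ROM sentence can therefore be read as 4 directions (flexion, extension, rotation to each side), 5 (adding lateral flexion once) or 6 (lateral flexion to each side).

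The Statistical Analysis Plan describes the comparisons as follows: "Evaluations were made both within the group before and after treatment (TO) and also for intergroup before and after treatment". One level applies to all of them: "In calculations, 0.05 was taken as the level of significance". The document contains no primary or secondary outcome, no testing order, no adjustment for multiple tests and no rule for concluding efficacy.

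**The concern.** The title asks one question: does capacitive-resistive therapy work for myofascial pain? The plan offers many tests that could be taken as the answer and ranks none of them. It does not say whether SF-36 is tested by scale, ROM by direction, or PPT at more than one site. Nothing in it would prevent a single SF-36 scale or ROM direction with p below 0.05 from being presented as evidence of efficacy when both pain measures show no difference. A reader holding only this document could not tell a planned confirmatory result from one picked afterwards.

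The harmful error is a false result in favour of the active device, so that is the error rate to look at first. The within-group tests add to the problem because they share the 0.05 level. The Treatment section has both arms exercising, so improvement within the active arm cannot isolate the effect of the device.

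**Working it through.** **Plan's own figure.** The only stated figure is the per-test level of 0.05, and one test at that level gives 5% (2.5% in each direction). There is no stated overall error rate, power or sample-size calculation to reproduce.

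**Inputs from the document.** Level 0.05; five instruments; eight SF-36 scales; 4 to 6 ROM directions depending on the reading; 36 participants in two groups.

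**Assumptions.** Tests are two-sided. Each outcome has one post-treatment between-group test. All pairs of test statistics share a common correlation r, with each outcome signed so that positive favours active. The split is 18 per arm. The document gives no correlations.

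**Number of tests.**
- One per instrument: k = 5.
- By scale and direction: VAS 1 + NDI 1 + PPT 1 + SF-36 8 + ROM 4 to 6, so k = 15 to 17.
- Pain measures only: k = 2.

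These counts leave out within-group tests, baseline between-group tests and any further PPT site.

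**Formulas.** For equicorrelated standard normal statistics, with Φ and φ the standard normal distribution and density and c = 1.96:
- favouring active: 1 − ∫ Φ((c − √r·u)/√(1−r))^k φ(u) du
- either direction: 1 − ∫ [Φ((c − √r·u)/√(1−r)) − Φ((−c − √r·u)/√(1−r))]^k φ(u) du

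At r = 0 these reduce to 1 − 0.975^k and 1 − 0.95^k.

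**Chance of at least one nominally significant result with no true effect (favouring active / either direction):**

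| k | r = 0 | r = 0.5 | r = 0.7 | r = 0.9 |
|---|---|---|---|---|
| 2 | 4.9% / 9.8% | 4.5% / 9.1% | 4.2% / 8.3% | 3.5% / 7.0% |
| 5 | 11.9% / 22.6% | 9.2% / 18.3% | 7.4% / 14.8% | 5.1% / 10.2% |
| 17 | 35.0% / 58.2% | 19.4% / 38.6% | 13.5% / 27.1% | 7.4% / 14.9% |

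The r = 0 column is an upper reference among the correlations tried. It is unlikely here, because scales of one questionnaire and directions of one measurement come from the same patients.

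**Check with t tests.** In 100,000 simulated trials with 18 per arm, the either-direction rates were 22.8% (r = 0) and 18.6% (r = 0.5) for k = 5, and 58.2% and 39.4% for k = 17. The normal approximation is adequate.

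**Power cost of adjusting across all outcomes.** For a two-sample t test with 18 per arm there are 34 degrees of freedom and the noncentrality is d × √(18/2) = 3d. Solving for 80% power:
- level 0.05: d = 0.96 SD
- first Holm step for 5 tests, 0.05/5 = 0.01: d = 1.20 SD
- first Holm step for 17 tests, 0.05/17 = 0.0029: d = 1.36 SD

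At a true difference of 0.96 SD, power at those three levels is 80%, 57% and 39%.

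**The case against.** The strongest reply is that the document never offers 5% as an overall error rate. It states a significance level, and that level is correct for each test. This stands: a reader might infer that the plan contradicts its own error rate, but it does not. The figures above show how far the chance of some positive result exceeds that of one test.

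It can also be said that the title and the Outcomes section point to pain, so only two tests matter. On that reading the inflation is modest: about 4% to 5% favouring active, for correlations from 0.7 down to 0. But this is inference from context. The document does not call pain primary and does not choose between VAS and algometer.

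The larger figures rest on assumption. Having eight SF-36 scales does not mean that each is tested, and the 58% at 17 tests also needs independence, which is implausible. Neither should be read as the plan's actual error rate.

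A reader might add two further complaints, and neither is supported:
- Choosing each test by a normality check might seem to inflate error further. The selection rule is stated, and in simulation with normal data and 18 per arm the null error was 5.1%.
- The past tense and the date 17.03.2020 might suggest that the outcome data had already been seen. The document gives no date for the last assessment or for unblinding, and says that the assessor stayed blinded until data collection ended.

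Finally, the registry record, not available here, may name a primary. If it does, much of the repair is a cross-reference. The omission from this document remains.

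**Conclusion.** The omission is certain on the face of the document; its size depends on assumptions. The ranges of 9% to 19% favouring active and 18% to 39% in either direction rest on 5 to 17 post-treatment between-group tests, a common correlation of 0.5 and no true effect on any outcome. At 0.7 they become 7% to 14% and 15% to 27%. Even with five tests and correlation 0.9, the rate is about double that of a single test. The two-measure pain reading is the mildest case.

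A reader might infer that the trial had no primary outcome at all, or that results were selected. The document supports neither. It shows only that this plan, taken alone, does not identify the confirmatory result.

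**What to change.** Amend the Statistical Analysis Plan to:
- name one primary pain outcome, VAS or PPT, consistent with any registered primary, with one post-treatment between-group test of it at two-sided 0.05;
- test the other pain measure and NDI only if the primary is significant, by Holm or in a fixed sequence;
- report SF-36 scales and ROM directions, each direction listed, as exploratory, with estimates and 95% confidence intervals;
- state that within-group and baseline tests do not support an efficacy claim;
- state whether the primary was fixed before unblinded data were seen and, if it was not, label the result post hoc or apply Holm across all listed between-group outcomes.

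**Cost.** If the primary was fixed in time, the change is wording only. In either case, a nominally significant secondary can no longer carry the efficacy claim. If the primary was chosen after unblinding, naming it now does not restore 5%. Holm across all outcomes would then raise the difference detectable with 80% power at the first step (18 per arm assumed) from 0.96 SD to 1.20 SD for 5 tests or 1.36 SD for 17. No clinical procedure changes and no new data are needed.
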